13. SAFETY ANALYSES

All safety analyses will be based on the safety population.

13.1 Extent of Exposure

The following exposure and compliance parameters will be summarized descriptively:

- Total number of days exposed, defined as (date of last dose of study drug - date of first dose of study drug) + 1.
- Number of doses administered, calculated from the subject dose diary including in-clinic doses. If a subject is exposed to study drug for more than 1 day, and returns no diary records, then the total number of doses is regarded to be missing. Otherwise, for any day for which there is no diary record, it is assumed that no study drug was administered at home.
- Grams (g) of study drug administered, total and average per day. Drug administered is calculated as the summation of the difference between dispensed weight and returned weight for all returned tubes. Unreturned/unopened tubes will be assumed unused and will be included as 0 gram in amount drug used calculation.
- Percent compliance will be calculated as the $(\text{date of last dose} - \text{date of first dose} + 1 - \text{number of missed doses}) / (\text{date of last dose} - \text{date of first dose} + 1) * 100$. Number of missed doses will be based on data from the summary missed doses form.
- Subject compliance, defined as $\geq 80.0\%$ compliance while enrolled in the study. If the percentage of study medication compliance cannot be computed, the subject is assumed to be less than 80% compliant.

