5.4 Compliance with Study Drug Administration

At Baseline, study staff will provide the subject and/or caregiver with detailed instructions concerning protocol requirements and use of study drug. Additionally, subjects and/or caregivers will be asked to complete a daily diary with the time of each application of study drug, except on study visit days. At each post-Baseline study visit, study staff will review use of study drug, as applicable, with the subject. Subject compliance will be assessed via study diary completion.

When subjects are dosed at the site, they and/or their caregivers will apply the study drug under supervision of the study staff. The date and time of each dose administered in the clinic will be recorded in the source documents. In clinic doses are not recorded in the subject's daily diary. The study drug and study subject identification should be confirmed at the time of dosing by a member of the study site staff other than the person dispensing the study drug.

At the time of dispensing study drug to each subject, site personnel will weigh the tubes to be dispensed with the cap on and will record the weight of all tubes dispensed at each visit in the drug accountability logs.

Subjects and/or caregivers will be instructed to bring all used and unused tubes with them to each study visit. Site personnel will weigh the returned tubes (used and unused) with the cap on and record the weight in the drug accountability logs. If a tube has been lost, discarded, or forgotten by the subject, then the site personnel will make a notation of this on the drug accountability logs. Forgotten tubes should be returned by the subject at the next study visit. Tubes of study medication dispensed at the most recent prior visit which remain unopened (the foil cap on the tube remains fully intact/undisturbed) may be re-dispensed to study subjects at the current visit. Unopened tubes may only be re-dispensed once. Opened, partially used tubes or tubes with

foil overlay removed are not to be re-dispensed to study subjects. If there is any question as to re-dispensation, sites should issue new tubes of study medication to the subject(s).

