6.6 Virtual Assessments

In the event that a subject cannot attend their regularly scheduled study visits in person due to a COVID-19-like situation necessitating a limit on in-person contact, the Investigator may perform safety and efficacy assessments by phone or video. Source documentation should note if the visit was performed by phone or video. The Investigator may use the technology platform that is currently available to them. Suggested platforms include Apple FaceTime, Zoom for Healthcare, Facebook Messenger video chat, Microsoft Teams, Google Hangouts video, and Skype. Additional details should be included in source documentation, as detailed in the Study Reference Manual.

If the subject can only be contacted by phone, the following should be assessed or performed:

- AEs
- Concomitant Medications
- Reminder to complete diary
- Instruction not to discard empty tubes of study drug

If the subject or caregiver has video capabilities, the following items should be assessed or performed:

- AEs
- Concomitant Medications
- vIGA-AD™ assessment (excluding subject's scalp)
- %BSA affected calculation (excluding subject's scalp)
- EASI (excluding subject's scalp)
- LTS (Investigator assessment)
- Application of study drug by the subject
- Completion of the PP-NRS itch scale – The subject can verbally indicate the answer which the study coordinator will document in the source document.
- Reminder to complete diary
- Instruction not to discard empty tubes of study drug

The reason that assessments cannot be completed during a virtual assessment (i.e., labs, vital signs, physical exams, etc.) must be noted (e.g., COVID-19) and the missed assessments will be recorded as protocol deviations.

7 Timing of Procedures and Assessments

This section lists the procedures and assessments to be performed at scheduled timepoints during the study as outlined in the Schedule of Assessments ([Table 1](#)). Information on study procedures and assessments is provided in Section [6](#).

- Any change in timing or any addition of a timepoint(s) for any planned study assessment must be documented in a “Note to File,” which is approved by the relevant Sponsor study team member and then archived in the study Sponsor and site study files; this will NOT constitute a protocol amendment.
- The IRB/IEC will be informed of any safety issues that require alteration of the safety monitoring scheme or amendment of the ICF.

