7.8 Unscheduled Visit

Subjects may have an unscheduled visit for AE follow-up, study drug dispensation, make-up for a missed visit, or other reason. The following assessments may be performed as needed:

- Brief physical examination

- Urine pregnancy test (females of child-bearing potential)
- Blood sample collection for clinical laboratory tests (serum chemistry, hematology, diagnostic tests)
- Urinalysis
- Vital signs measurement
- Dispense and / or collect study drug
- Review instructions on how to apply study drug
- AE recording
- Concomitant medication recording
- Dispense and / or collect subject diaries
- vIGA-AD™ score (excluding subject's scalp)
- %BSA affected calculation (excluding subject's scalp)
- EASI (excluding subject's scalp)
- Assessment of itch (PP-NRS)
- Review subject diaries for treatment compliance

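### SAP 13.1 counts every unreturned tube as unused, so opened tubes that never come back add 0 g and a treated subject who returns none is summarised at an impossible 0 g

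*SAP*

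**What the plan says.** SAP 13.1 lists total and average daily grams among the exposure summaries. The total is the "summation of the difference between dispensed weight and returned weight for all returned tubes". For the rest the rule is: "Unreturned/unopened tubes will be assumed unused and will be included as 0 gram in amount drug used calculation". There is no exception for a tube that was opened before it went missing, and no missing-data rule for a subject who returns nothing.

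The same list treats the diary differently. A subject exposed for more than one day who "returns no diary records, then the total number of doses is regarded to be missing". For partial gaps the rule is different again: "Otherwise, for any day for which there is no diary record, it is assumed that no study drug was administered at home".

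The protocol expects non-return. Section 5.4 tells sites what to note "If a tube has been lost, discarded, or forgotten by the subject", and section 6.6 includes among the items for remote contacts: "Instruction not to discard empty tubes of study drug". It also works against non-return: under section 5.4 subjects are to "bring all used and unused tubes with them to each study visit", and section 7.8 allows sites at unscheduled visits to "Dispense and / or collect study drug".

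Average grams per day is the x-axis of two figures in SAP 12.2, against Day 1 Cmax and Day 1 AUC.

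**The concern.** Zero is the right value for a tube known to be unopened. For a tube whose contents were never weighed it is a guess, and for an opened tube it is wrong. An empty tube that is thrown away is the worst case: the true value is close to the full tube and the recorded value is 0 g.

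The rule also produces a value that the plan rules out elsewhere. SAP 8 admits to the safety population only subjects with at least one application, and Protocol 7.2 has the Day 1 dose applied under supervision. A subject dosed on Day 1 and then lost to follow-up may return no tubes, yet can have Day 1 concentrations. That subject would enter the summary at 0 g and be plotted at 0 g/day beside real Day 1 exposure values.

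Protocol 1.1.2 describes a maximal use study, meant to measure systemic exposure when absorption is likely to be greatest. Grams applied are the direct description of how much drug was used. A rule that can only understate them, in cohorts of 10 to 12, weakens that description.

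**Working it through.** The plan gives no figure to reproduce here, so the SAP 13.1 rule was applied directly and compared with true use.

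**Inputs from the documents**
- Nominal tube content: 30 g (Protocol Synopsis, Investigational Product).
- Treatment length: 27 days (Protocol 3.2). With the Day 28 visit allowed ±2 days and intended doses equal to visit day minus 1 (Protocol 3.3), the range is 25 to 29.
- Cohort size: about 12, minimum 10; about 36 overall (SAP 5).

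**Assumptions**
- SAP 13.1 does not define the denominator for average grams per day. Treatment days are used here.
- Use per subject and the rate of non-return are not given. Values below that depend on them are illustrations.

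**Step 1: the wording.** The slash in the rule could mean unreturned or unopened, or unreturned and unopened. The result is the same either way: the sum runs over returned tubes only, so an opened, unreturned tube adds nothing.

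**Step 2: one opened tube not returned.** The understatement equals the amount used from it, at most 30 g.
- Per day: 30/27 = 1.11 g; range 30/29 = 1.03 g to 30/25 = 1.20 g.
- Two tubes: 60 g, or 60/27 = 2.22 g/day.
- Half a tube used: 15/27 = 0.56 g/day.
- If a subject fully used k tubes and one is missing, the share missed is 1/k: 50% for 2 tubes, 25% for 4, 10% for 10, 5% for 20.

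**Step 3: effect of one such tube on the mean total.** At most 30/n: 30/12 = 2.5 g; 30/10 = 3.0 g; 30/36 = 0.83 g.

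**Step 4: a subject who returns no tubes.** The rule gives 0 g whatever was used; for example, four fully used tubes are 4 × 30 = 120 g in truth and 0 g in the summary. If all n subjects used the same amount g, the reported mean is (n − 1)g/n, a loss of 1/n.

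| Group | n | Loss in mean |
|---|---|---|
| Age cohort, planned | 12 | 8.3% |
| Age cohort, minimum | 10 | 10.0% |
| Overall | 36 | 2.8% |

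The group minimum becomes 0 g in every case.

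**Step 5: a general loss rate.** If a share p of used tubes is not returned and use per tube is equal, total grams are low by p. Assumed rates of 2%, 5% and 10% give totals 2%, 5% and 10% low. This shows the scale only; it is not evidence of the actual rate.

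**Step 6: how tubes can stay unreturned.** Protocol 5.4 sends forgotten tubes to the next visit. One forgotten at Day 8 can be weighed at Day 28. One forgotten at Day 28 has no scheduled collection afterwards, because the Follow-up list in Protocol 7.6 does not include study drug. An unscheduled visit is possible but optional.

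**The case against.** The strongest reply is that little depends on grams. They are not an endpoint, there is no hypothesis test, and Cmax and AUC do not use them. SAP 13.1 bases compliance on missed doses, so the 80% flag does not move. This is right, and it limits the matter to one descriptive summary and two figures. Those figures also plot study-average use against Day 1 exposure, so their x-axis is not the Day 1 dose even when every tube comes back.

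Second, non-return may be rare. Subjects are told to bring all tubes, sites log what is missing, and subject listings would show a 0 g total. The frequency is indeed unknown. But a listing that lets a reader spot the error does not correct the mean, the minimum or the plotted point.

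Third, Protocol 1.1.2 describes maximal use through severe disease or large affected area and does not mention grams, and understatement cannot make use look more maximal than it was. That is fair as to direction. Even so, a total known to be too low misdescribes use and overstates exposure per gram.

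Fourth, the diary parallel is partial: for gaps within a returned diary the SAP also assumes no dose. This stands, so the inconsistency within SAP 13.1 concerns total non-return only.

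Fifth, Protocol 10.6 rules out imputation, which counts against adding 30 g per missing tube. It counts equally against adding 0 g. The upper bound is best kept as an optional, labelled sensitivity figure, since it also adds 30 g for missing tubes that were never opened.

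**Conclusion.** The concern holds. SAP 13.1 states a rule that gives a wrong value in a situation the protocol foresees, and for a treated subject with no returned tubes the value is impossible. The error from this rule is always downward: up to 30 g per opened tube not returned (about 1.1 g/day over 27 days), and the whole of a subject's use if nothing comes back. One such subject costs 8.3% to 10% of a cohort mean under equal use and sets the minimum to 0 g.

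The actual bias cannot be stated, because the rate of non-return and the expected use per subject are not in the documents. The consequences are limited to the exposure summary and two figures. It should be corrected, but it does not threaten the primary PK or safety results.

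**What to change.** In SAP 13.1:

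1. Score 0 g only for tubes that were returned unopened.
2. If a subject returns no used tube (none at all, or only unopened ones), set total and average grams to missing, in line with the existing rule for a subject with no diary, and leave the subject out of the two SAP 12.2 figures that use grams.
3. If some tubes are unreturned, keep the subject and label the returned-tube total as a minimum. Optionally, present beside it an upper bound that adds the nominal 30 g per unreturned tube, marked as a sensitivity figure. The 30 g is nominal because tubes are weighed whole with the cap on.
4. Report the number of subjects and tubes affected.

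Decide return status after the subject's last visit, so that a tube forgotten once and brought later counts as returned. State the denominator for average grams per day at the same time.

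The cost is a wording change, one extra summary row and a few missing values. The calculation already needs dispensed and returned weights, so a tube with the first and not the second can be identified. Whether the site's note of a lost or discarded tube also reaches the database cannot be seen from the protocol or SAP.

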13.2 Adverse Events

All AE summaries will be restricted to treatment-emergent AEs (TEAEs), which are defined as those AEs that occurred after dosing and those pre-existing AEs (prior to first application of study drug) that worsened during the study. If it cannot be determined whether the AE is treatment-emergent due to a partial onset date, then it will be counted as such. The one exception will be the summary of Any AE which will include AEs not considered treatment-emergent. The summary of Any AEs will be reported in the Overall Summary of Adverse Events.

Verbatim terms in the eCRFs will be mapped to SOCs and PTs using MedDRA (Version 24.0).

For subjects not rolling over to the OL-LTE safety study, all reported AEs will be included in the open-label maximal use summaries. For subjects rolling over to the OL-LTE safety study, all

AEs with an onset date on or before the Week 4 visit date will be included in the open-label maximal use summaries.

Imputation of Start and End Dates of Adverse Event

To calculate duration of AEs, the following rules will be used where applicable to impute partial or completely missing start dates or end dates:

- If only the day is missing for a start date, the 1st of the month will be imputed. If the new estimated date falls before the date of first dose, while the known month and year match the month and year of the first dose, the date of first dose will be used as the new estimated date. The AE will be considered as a treatment-emergent AE (TEAE).
- If only the day is missing for an end date, the last day of the month will be imputed. If the new estimated date falls after the date of last study visit, the date of last study visit will be used as the new estimated date. Last study visit is defined as the Week 4 visit for those who elect to participate in the OL-LTE safety study, or the Week 5 Follow-up Visit for those who fail to qualify for participation in the OL-LTE safety study, or who qualify to participate but ultimately elect not to enroll.
- If both the day and the month are missing for a start date or end date, no imputation will be used, and the duration will not be calculated. However, if the year of start is the same or greater than the year of the first dose date, the AE will be considered as a TEAE.
- If the start date or end date is completely missing, duration will not be calculated. However, an event with completely missing start date will be considered as a TEAE.

Imputation of missing relationship and/or missing severity

If relationship to treatment is missing, the event will be conservatively treated as related to study drug.

If severity is missing and the AE is reported as serious and fatal, severity will be imputed as CTCAE=5. If severity is missing and the AE is reported as serious and not fatal, severity will be imputed as CTCAE=4. If severity is missing and the AE is not reported as serious, severity will be imputed as CTCAE=3.

All AEs will be listed by subject, detailing the verbatim term given by the Investigator, the SOC, PT, onset date, end date, common terminology criteria for adverse events (CTCAE) grade, outcome, relationship to study drug, action taken with study drug, other action taken to treat the event, seriousness, and criteria for seriousness. Serious AEs (SAEs), TEAEs related to study drug, TEAEs leading to study drug discontinuation, and TEAEs leading to study discontinuation will also be listed separately. The following adverse events of special interest (AESIs) will be identified and listed separately: contact dermatitis, follicular events, and headache.

All AEs will be summarized by treatment as incidence rates of:

- Any AE

TEAEs will be summarized as incidence rates of:

- Any TEAE
- Any treatment-related TEAE
- Any TEAE leading to study drug discontinuation
- Any TEAE leading to study discontinuation
- Any TEAE by maximum CTCAE Grade
- Any treatment-related TEAE by maximum CTCAE Grade
- Death
- Any treatment-emergent AESIs
- Any serious TEAEs

At each level of summarization, a subject will be counted once if he/she reported one or more events. The severity of TEAEs and relationship to study drug will be summarized in a similar manner. For summaries of relationship to study drug, a subject will be classified according related or not related. For summaries of TEAE CTCAE grade, a subject will be classified according to the worst grade.

For treatment-emergent AESIs, summarization will be more extensive, reflecting the more detailed information collected. Information summarized will include number of events per subject, earliest onset day, duration (in days), causality, grade, and seriousness of AESIs, outcome, actions taken with study drug, assorted physical characteristics of the AESIs, and demographic/baseline characteristics and vIGA-AD™ status of the subjects experiencing them. Each type of AESI will be summarized separately. If a subject has more than one treatment-emergent occurrence of an AESI, the subject's maximum duration, highest levels of causality and seriousness, maximum grade and generally the most extreme level of each characteristic will be summarized. If an AESI was ongoing at end of study (EOS), it will not be included in the duration summary.

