Study drug application instructions will be reviewed at all post-baseline clinic visits and during the planned study phone call. The time of the dose application and assessments will depend on the time of the clinic visit. Therefore, the timing of the clinic visit may lead to a change in the subject's chosen dosing time for that day.

On Day 28 of this study, a final PK sample will be collected and subjects will have the option to enroll in a separate open-label long-term safety study for an additional 48 weeks. Subjects who choose not to participate in the open-label long-term safety study or who fail to qualify for participation in the open-label long-term safety study will complete a Follow-up Visit (Day 35) approximately 7 days after the end of treatment in this study. Subjects who withdraw from the study before Day 28 will complete an Early Termination Visit as their final visit and are not eligible for the open-label long-term study. Subjects that complete an Early Termination visit will not complete a Follow-up visit.

Study duration for subjects who complete this study and who fail to qualify for participation in the open-label long-term safety study, or who qualify to participate in the open-label long-term safety study but elect not to enroll in that study is approximately 9 weeks in total. Study duration for subjects who complete this study

and are eligible and decide to participate in the open-label long-term safety study is approximately 8 weeks in total.

Efficacy assessments will include v-IGA-AD™ score, %BSA affected, EASI, and PP-NRS. Safety assessments will include AEs, clinical laboratory tests, physical examination, vital signs, and LTS.

Pharmacokinetics will be assessed at Days 1 and 28. The screening blood sample will be used for baseline PK if the subject is enrolled. Blood samples for PK should not be collected from any anatomic site where study drug has been applied in order to minimize potential contamination.

Refer to Section 6 for descriptions of study procedures and assessments and Section 7 and the Schedule of Assessments ([Table 1](#)) for timing of procedures and assessments

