7.6 Visit 5; Follow-Up (Day 35 ±3 Days)

Subjects who do not enroll in the open-label long-term safety study will return to the study site 7-10 days after Day 28 to complete follow-up assessments as follows:

- Brief physical examination
- If needed, blood sample collection for clinical laboratory tests
- If needed, urinalysis
- Vital signs measurement
- AE recording
- Concomitant medication recording
- vIGA-AD™ score (excluding subject's scalp)
- %BSA affected calculation (excluding subject's scalp)
- EASI (excluding subject's scalp)

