8.3 Time Period and Frequency for Event Assessment and Follow-Up

8.3.1 Adverse Event Reporting

All AEs will be collected from the time of signed informed consent until the final visit.

Any AEs assessed as related to study participation (e.g., protocol-mandated procedures, invasive tests, or change in existing therapy) will be collected from the time a subject consented to participate in the study up to and including any follow-up contact.

All SAEs will be recorded in the CRF and reported to the Sponsor within 24 hours via email or phone (refer to the [Medical Monitor / Sponsor Information Page](#) for contact information) (see Section [8.4](#)).

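### TEAE incidence uses different end dates by rollover status, with no table on a common window; the effect is modest and easily removed

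*SAP*

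**What the plan says.** SAP section 13.2 sets the counting rule by what the child does after Week 4. For children outside the extension, "For subjects not rolling over to the OL-LTE safety study, all reported AEs will be included in the open-label maximal use summaries". For children who enter it, "AEs with an onset date on or before the Week 4 visit date will be included in the open-label maximal use summaries". The same section defines TEAEs as "those AEs that occurred after dosing and those pre-existing AEs (prior to first application of study drug) that worsened during the study". That definition has a start and no end relative to the last dose.

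The length of the open-ended window comes from the protocol. Section 8.3.1 says "All AEs will be collected from the time of signed informed consent until the final visit". For completers outside the extension the final visit is Visit 5: "Subjects who do not enroll in the open-label long-term safety study will return to the study site 7-10 days after Day 28" (Protocol section 7.6). Early terminators stop sooner: "Subjects that complete an Early Termination visit will not complete a Follow-up visit" (Protocol section 3.1).

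Protocol section 3.3 sets the number of intended doses at the study day of the Day 28 visit minus one, and SAP section 7 labels Week 4 as end of treatment. The follow-up week is therefore off drug.

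TEAE incidence is a primary endpoint (Protocol section 2). SAP section 13.2 reports it as the share of children with at least one event, and SAP section 6 requires all summaries by age group and overall. Neither document plans a common cut-off, a separate follow-up table or an exposure-adjusted rate.

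**The concern.** A proportion of children with at least one event depends on how long each child is observed. Here the length is set by a status that arises after treatment. To enter the extension a child must have taken at least 80% of intended doses, must qualify, and must choose to enrol (Protocol sections 3.1 and 3.3). Children outside it are a selected group, and if they complete treatment they contribute about a week more than the others, all of it off drug. Early terminators form a third group whose window ends at the Early Termination visit.

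All three groups share one denominator. Two age cohorts with the same risk per day would show different TEAE percentages if their rollover rates differed. The overall percentage would also mix events on treatment with events after stopping, in a proportion that the planned AE tables do not show.

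**Working it through.** There is no planned figure to reproduce. The sample size of about 36 (3 × 12) rests on feasibility, and no TEAE rate is assumed. The check is therefore an illustration of size.

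**Inputs from the documents**
- Rollover window: first dose to the Week 4 visit, nominally 28 days (Day 28 ±2, so Day 26 to 30).
- Window for completers who do not roll over: to the follow-up visit, nominally 35 days. The heading of Protocol section 7.6 gives Day 35 ±3 (Day 32 to 38), while its text implies Day 35 to 38. The two need reconciling, because they set the longer window.
- Reference risk: 54% over 12 weeks (84 days) for the 1% once-daily arm of the earlier dose-finding study (Protocol section 1.2). I read this as the share of subjects with a TEAE. That study enrolled adults and adolescents (Protocol section 1.1.1).

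**Assumptions**
- The hazard is constant and does not change when drug stops.
- The rollover fraction *f* is not given, so it is varied from 0 to 100%.
- Early terminators are ignored.

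**Step 1: window ratio.** Nominal: 35/28 = 1.25. Across the visit windows it runs from 32/30 = 1.07 to 38/26 = 1.46.

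**Step 2: risk by window.** h = −ln(1 − 0.54)/84 = 0.00924 per day, and risk(d) = 1 − exp(−h·d).
- risk(28) = 22.8%
- risk(35) = 27.6%
- Gap between groups = 4.8 points (4.84 before rounding)

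**Step 3: pooled incidence.** Pooled = f × 22.8% + (1 − f) × 27.6%. With a common Week 4 cut-off it would be 22.8% for any *f*.

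| Rollover | Pooled under the SAP | Excess, points | Excess, children of 36 |
|---|---|---|---|
| 0% | 27.6% | 4.8 | 1.7 |
| 50% | 25.2% | 2.4 | 0.9 |
| 75% | 24.0% | 1.2 | 0.4 |
| 90% | 23.3% | 0.5 | 0.2 |
| 100% | 22.8% | 0 | 0 |

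**Step 4: contrast between cohorts.** At equal daily risk, the spurious difference is the difference in rollover fraction times 4.84 points. For 90% against 50% it is 0.40 × 4.84 = 1.9 points.

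**Step 5: sensitivity to the 28-day risk p.** risk(35) = 1 − (1 − p)^(35/28).

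| p at 28 days | At 35 days | Gap, points |
|---|---|---|
| 10% | 12.3% | 2.3 |
| 20% | 24.3% | 4.3 |
| 30% | 36.0% | 6.0 |
| 40% | 47.2% | 7.2 |
| 50% | 58.0% | 8.0 |

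**Step 6: sampling error for scale.** 1.96 × √(0.228 × 0.772/n) is 13.7 points for n = 36 and 23.7 points for n = 12. In a cohort of 12, a 4.8-point gap is 12 × 0.0484 = 0.6 of a child.

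**The case against.** The case for leaving the rule alone has real substance.

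- **The rule has a reason.** Children who roll over may receive more drug in another study, so their later events belong there. For the rest, counting everything collected is the inclusive choice for a paediatric safety endpoint. This stands, and it is why the all-reported summary should stay.
- **Nothing is tested.** The study is single-arm with no hypothesis, and Protocol section 10.4.2 rules out formal safety comparisons. SAP section 9.1 also tabulates how many children enter the extension, so a reader can see the rollover rate. This stands and limits the point to how displayed percentages are read.
- **The effect is below sampling error.** True at these sizes. But the window difference is systematic and avoidable, and imprecision is no reason to keep it.

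Three stronger readings are tempting, and the documents do not support them.

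- A reader might infer that on-treatment and post-treatment events cannot be told apart. SAP section 13.2 lists every AE by subject with its onset date, so with about 36 children this can be done by hand. What is missing is a table.
- A reader might infer that any eczema flare after stopping would count as treatment-emergent. Protocol section 8.1.1 excludes expected signs of the disease under study from the AE definition, so only a flare more severe than expected would count.
- A reader might infer a gap of 8 to 11 points between cohorts. That takes a 28-day risk of 50%, which becomes 58.0% at 35 days and 61.0% at 38 days, and also no rollover in one cohort against full rollover in another. A 50% risk at 28 days implies 1 − 0.5³ = 87.5% over 12 weeks, against the 54% in the documents, and nothing suggests so extreme a split in rollover.

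**Conclusion.** The point holds as a modest defect in presentation. Crude TEAE incidence under SAP section 13.2 depends partly on rollover status, because the counting window does and the TEAE definition has no end.

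On the documents' only usable reference rate the two main groups differ by about 4.8 points. How much of that reaches the pooled figure depends on rollover, and at high rollover almost none does. The age-cohort display is more exposed, but only if rollover differs between cohorts.

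These sizes rest on a constant hazard carried into the off-drug week. Protocol section 1.2 says plasma concentrations are highest in the first week and then fall, so for drug-related events the added week may bring fewer events than shown. The reference rate comes from older subjects, and the rollover fraction is unknown. The inequality of the windows needs none of these assumptions. The change is worth making because it is cheap and TEAE incidence is a primary endpoint.

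**What to change.** In SAP section 13.2:

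1. Add TEAE incidence tables, overall and by age cohort, with one cut-off for every child: onset from first dose through the Week 4 visit date, or the Early Termination visit date for early terminators. Use these tables for incidence and for the age-cohort display. The cut-off is the one the SAP already applies to children who roll over.
2. Tabulate events with onset after the Week 4 visit separately, with the children attending Week 5 as denominator.
3. Keep the all-reported-AE summary, the SAE reporting and the listings unchanged, so that no event leaves the primary safety reporting.

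The cost is SAP wording and a few extra tables. No new data and no change to visits or care are needed. What remains unequal is the shorter follow-up of early terminators. The common window will also still contain some off-drug days for children who stop drug but stay in the study for safety assessments, as Protocol section 4.6.1 allows.
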